"Physiological" insulin scheme vs "Traditional" scheme for glycemic control in non-critical hospitalized patients with Type 2 Diabetes Mellitus: Controlled Clinical Trial

Registration number: NCT03350984

Date: 02/08/2019

MATERIAL AND METHOD

TYPE OF STUDY:

- Clinical controlled trial, randomized, not blinded, comparative between 2 groups.

WORKING UNIVERSE

- Patients with diabetes mellitus type 2.

SAMPLING FRAME

- Hospitalized patients in the medical and surgical services of the hospital: internal medicine, traumatology and orthopedics and general surgery of the General Hospital of León not critical with diabetes mellitus type 2.

SAMPLE SIZE

- It was determined a minimal sample size of 33 patients per group plus 7 extra patients in each group to compensate possible losses, which gave a total of 40 per group. The sample size was determined by the formula: $n=(Z\alpha/2+Z\beta)^2 * (p_1(1-p_1)+p_2(1-p_2)) / (p_1-p_2)^2 \cdot (36)$ It was considered the probability of making a mistake type 1 (α) of 0.05, a statistical potential ($1-\beta$) of 0.80 and a difference of 25% in the rate of hypoglycemia in reference with the one reported in the meta-analysis of Christensen MB et al(27), for both treatments in a bicaudal way in the distribution curve.

SAMPLING TYPE

- Randomized systematic sampling. The assignment to the treatment schemes was made using a randomized numbered table generated by a computer. If more of one patient arrived to the hospital at the same time, they were randomized in order of the service they arrived: Internal medicine (IM): 1st, Traumatology and orthopedics (TyO): 2nd and General surgery(GS): 3rd, and in base of the number of bed from lower to higher.

INCLUSION CRITERIA

- Patients older than 18 years old, with diagnosis of diabetes type 2 with central fasting glucose before randomization between 140mg/dl and 400mg/dl.
- Patients that were diagnosed at admission with DM2 with HBA1>6.5% and fasting glucose >126mg/dl (isolated hyperglycemia >200mg/dl was not considered as a diagnostic parameter because of the stress conditions, metabolic response to the base pathology or steroid exposition that can alter the glycemia values in hospitalized patients).
- Patients in not critical state.
- Patients with a diet for diabetic patient per oral administration at least 3 times

daily.

EXCLUSION CRITERIA

- Parenteral nutrition and continuous enteral nutrition by nasogastric tube.

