The descriptive statistical analysis was carried out in the following way: for the qualitative variables proportions and percentage rates (%) were reported; for the quantitative variables, mean and standard deviation or median and interquartile range (Q1 to Q3) were reported according to the distribution of the data. The normality of the distribution was determined by the Kolmogorov-Smirnov test.

The univariate inferential analysis was performed using the chi-square test or Fisher's exact test for the qualitative variables, according to the distribution of the expected values in the contingency table. For the numerical variables, the t test was used for two independent samples or its non-parametric version, according to the nature of the distribution of the numerical data. A p value <0.05 was considered significant.

For the analysis of the treatment, the risk analysis model will be used with the calculation of the RR, RAR, RRR, its 95% Confidence Interval (95% CI) and the NNT was determined for the traditional scheme, once the data were concluded. The analysis was considered by protocol and by intention to treat.

RESULTS

PATIENTS OF THE STUDY

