A total of 111 hospitalized DM2 patients not critical to the study were evaluated. Of these, 35 did not meet the inclusion criteria and the 76 included participants were randomized into two groups. The recruitment of patients began on November 15, 2017 and ended on June 1, 2018. The "physiological" insulin group with 37 participants and the traditional group with 39 participants. Within the "physiological" group, 1 patient was eliminated before initiating the insulin regimen, presenting acute abdomen and requiring intensive therapy. Therefore, 36 patients in the "physiological" group and 39 patients in the traditional group began treatment, who entered the analysis for intention to treat. From the physiological group 6 patients did not conclude the treatment by discharge before the control and 2 patients due to poor adherence to the treatment. In the traditional group, 5 patients withdrew before the control, 1 patient due to poor adherence to treatment, 1 patient died before the control, and 1 patient was suspended due to critical condition. At the end of the study, 28 patients in the "physiological" group and 31 patients in the traditional group were completed in the analysis per protocol. In 20 (71.4%) patients in the first group and in 30 (96.8%) patients in the second group, treatment was completed until discharge.

POPULATION CHARACTERISTICS

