There was a significant difference in the sustained control of blood glucose that was reported in 20 (55.6%) of the cases in the physiological group compared to 30 (76.9%) of the traditional group (per protocol, RR: 0.74, 95% CI: 0.58 to 0.94, $p = 0.009$; by intention to treat, RR: 0.72, 95% CI: 0.51 to 1.01, $p = 0.049$).

The causes of failure of the sustained control were discharge before control in goals, progress to critical state, death before glycemic control, poor adherence to the protocol and suspension for sustained hypoglycemia. With the "physiological" scheme it was necessary to suspend or change by another scheme in 8 (22.2%) patients, in comparison with the traditional scheme where only the scheme was suspended or changed in 1 (2.6%) patient (by intention to treat, RR: 8.67, 95% CI: 1.14 to 65.92, $p = 0.011$). There were no adverse effects to the use of insulin in both groups.

OTHER RESULTS

If the suspension of the scheme is considered for sustained hypoglycemia of 8 patients in the physiological group vs 1 patient in the control group, a risk ratio of 8.67 (95% CI: 1.14 to 65.9) and a number necessary to harm of 5.09 was calculated (95% CI: 2.93 to 19.23) patients with the physiological scheme to produce 1 event of hypoglycemia.

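### One p<0.05 rule covers 19 tests in two unranked analysis sets with no named primary outcome, so an unprotected result is called significant while the outcome the trial was sized on is null

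*Combined protocol and SAP*

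**What the plan says.** The Statistical Analysis section gives one threshold: "A p value <0.05 was considered significant". On analysis sets it says "The analysis was considered by protocol and by intention to treat", without ranking them. No section names a primary outcome or a rule for multiple tests.

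The Sample Size section uses a two-proportion formula. It states "It was considered the probability of making a mistake type 1 (α) of 0.05", a power "of 0.80 and a difference of 25% in the rate of hypoglycemia", and a two-sided test ("for both treatments in a bicaudal way in the distribution curve"). The design alpha is therefore spent on one quantity, the hypoglycaemia rate.

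Results appear under the headings Effectiveness, Safety, Secondary and Other. Under Secondary Results the text states "There was a significant difference in the sustained control of blood glucose". This is the only outcome called significant in words.

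**The concern.** A single 0.05 threshold applied to many outcomes in two sets does not hold the overall false-positive rate at 5%. The sample-size text implies a confirmatory question, but the analysis plan gives it no priority. Followed as written, the rule lets whichever outcomes cross 0.05 carry the comparison between schemes, while the outcome that justified the sample size shows no detected difference.

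What is at stake is how the reported disadvantages of the physiological scheme are read: repeat hypoglycaemia, loss of sustained control and suspension. As reported, they look like three established and separate findings. The closing number needed to harm under Other Results adds to this, because it is computed from suspensions but worded as if it counted hypoglycaemic events.

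**Working it through.** **Inputs.** The ITT denominators are 36 v 39 and the per-protocol (PP) denominators 28 v 31 (Patients of the Study). Counts and p-values come from Effectiveness, Safety, Secondary and Other Results.

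**1. Reproducing the reported ITT results.** Chi-square is used where all expected counts are at least 5 and Fisher's exact test otherwise, following the plan's rule. Intervals are Wald intervals on the log RR.

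| Outcome | Counts | RR (95% CI) | p reported | p recomputed |
|---|---|---|---|---|
| Any hypoglycaemia | 15/36 v 15/39 | 1.08 (0.62 to 1.89) | 0.777 | 0.7771 (chi-square) |
| More than 2 events | 8/36 v 2/39 | 4.33 (0.98 to 19.07) | 0.041 | 0.0418 (Fisher) |
| Sustained control | 20/36 v 30/39 | 0.72 (0.51 to 1.01) | 0.049 | 0.0499 (chi-square) |
| Suspension or change | 8/36 v 1/39 | 8.67 (1.14 to 65.92) | 0.011 | 0.0118 (Fisher) |

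The RRs and intervals match, and the p-values match when cut to three decimals. Two of the three results below 0.05 have an RR interval that includes 1. For sustained control, Fisher's test would give 0.085.

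**2. Number of tests.** The comparisons with p-values are fasting, postprandial and morning glucose, days to control, any hypoglycaemia, more than 2 events, events per affected patient, share of mild events, sustained control, and suspension. That is 10. Nine are reported in both sets and suspension in ITT only: 9 × 2 + 1 = 19.

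**3. Family-wise error if independent.**
- 10 tests: 1 − 0.95^10 = 0.401
- 19 tests: 1 − 0.95^19 = 0.623

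The PP and ITT sets are nested and the outcomes correlated, so these are upper figures. The true rate is lower but above 5%.

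**4. Holm adjustment (recomputed p-values).**
- Ten ITT comparisons: suspension 10 × 0.0118 = 0.118; more than 2 events 9 × 0.0418 = 0.376; sustained control 8 × 0.0499 = 0.399. None survives. The reported p-values give 0.110, 0.369 and 0.392.
- Four patient-level binary ITT outcomes: suspension 4 × 0.0118 = 0.047 survives; more than 2 events 3 × 0.0418 = 0.125 does not; sustained control, 2 × 0.0499 = 0.100, is raised to 0.125 by the step-down rule and does not.
- All 19 tests, reported p-values: the smallest is PP sustained control, 19 × 0.009 = 0.171.

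**5. The sized outcome.** The risk difference is 15/36 − 15/39 = 0.417 − 0.385 = +3.2 points. SE = √(0.417×0.583/36 + 0.385×0.615/39) = 0.113, so the 95% CI is −19.0 to +25.4 points. The interval includes zero and, just, the 25-point difference used for sizing (reading the stated 25% as percentage points).

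**6. Overlap by count.**
- ITT failures of sustained control: 36 − 20 = 16 v 39 − 30 = 9.
- Patients who left the PP set: 36 − 28 = 8 v 39 − 31 = 8.
- Remainder: 16 − 8 = 8 v 9 − 8 = 1, which equals the suspensions.
- PP failures: 28 − 20 = 8 v 31 − 30 = 1, the same 8 v 1.

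Secondary Results also lists suspension for sustained hypoglycaemia among the causes of failed sustained control.

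**7. Number needed to harm.** 1/(8/36 − 1/39) = 1/0.1966 = 5.09. This is the suspension contrast. The same arithmetic for any hypoglycaemia gives 1/0.0321 = 31.2, from a difference whose interval includes zero.

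**The case against.** Several points on the other side stand.

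- A reader might infer that the trial declares three results significant. Only sustained control is so described; the other two meet the rule but carry p-values alone.
- A reader might infer that nothing survives correction. That depends on the family. The ten comparisons mix patient-level risks with an event-level proportion and a mean among affected patients only. In the four-outcome family suspension survives, and at 0.011 it is not borderline. PP sustained control (0.009) and PP more than 2 events (0.021) are not at the margin either.
- A reader might call the more-than-2 cut-off post hoc. It is not listed as an outcome in the methods, but the suspension rule under Management of Hypoglycemia, which concerns repeat events after a first one, may be its source. The documents do not settle this.
- Repeat hypoglycaemia and suspension are harm signals, and strict adjustment of harms risks missing them. Whether to adjust them is a judgement.
- Sustained control and suspension already sit under Secondary Results and the number needed to harm under Other Results. That helps, but no outcome is labelled primary, and sustained control is still called significant.

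On overlap, a reader might infer that the failures and the suspensions are the same patients. Only the counts agree. One traditional-group patient suspended for critical condition is listed among those who left the PP set, so the single traditional suspension could in principle be that person. Against this, Other Results attributes the 8 v 1 suspensions to sustained hypoglycaemia, and the PP exclusions account for the other listed causes of failure. The match by count stands; patient identity is not shown.

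**Conclusion.** The concern holds. It is a stated decision rule that leads to an unsound claim, not only a missing definition: sustained control is called significant at p=0.0499 with an RR interval of 0.51 to 1.01, in a trial sized on another outcome that is null at p=0.777. The family-wise error is at most about 40% over 10 comparisons and 62% over 19 tests, these being the values under independence. Whether suspension survives adjustment (0.118 or 0.047) turns on a family that the plan does not state. Sustained control and suspension are not independent evidence.

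This rests on reading the hypoglycaemia rate in the sample-size text as patients with at least one episode, as a formula for proportions requires, and on the ITT set as reported (36 v 39). The documents do not support two stronger readings: that the three results are false positives, or that the schemes are equivalent for hypoglycaemia. The interval of −19.0 to +25.4 points is too wide for the second.

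**What to change.** - Name at least one hypoglycaemic event, ITT, as the single primary test at two-sided 0.05. State that this was inferred retrospectively from the sample-size text, since results are already known.
- Label all other outcomes, and the whole PP set, secondary or exploratory. Give estimates, 95% CIs and nominal p-values, without the word significant. A separate ungated Holm procedure at 0.05 for the secondaries would not hold 5% overall (1 − 0.95² = 9.75% if independent).
- Keep repeat hypoglycaemia and suspension visible as harm signals.
- Report sustained control and suspension as overlapping by count, and confirm the patient-level overlap from the data.
- Describe the number needed to harm of 5.09 as referring to suspension of the scheme, not to one event of hypoglycaemia.

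The cost is rewording of the analysis plan and results, plus one check of existing patient data. The downside is that the secondary claims become weaker.

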Of the total patients analyzed for intention to treat, 34 (45.3%) patients were men and 41 (54.7%) women. According to the place of hospitalization, 18 (24%) were in the internal medicine service, 29 (38.7%) in traumatology and orthopedics and 28 (37.3%) in general surgery. The mean age of the patients was 57.83 ± 13 years. The average body mass index was 26 ± 5.1 kg / m². The mean random glucose at admission was 230.5 ± 70.2 mg / dL, the glycosylated hemoglobin level was $8.3 \pm 2.3\%$, and the serum creatinine was 1 ± 0.5 mg / dL. The treatment before admission was with oral hypoglycemic agents in 25 (33.3%) patients, with insulin in 25 (33.3%) patients, the combination of oral hypoglycemic agents and insulin in 12 (16%) patients and 13 (17.3%) patients. they received treatment or were diagnosed at the time of admission. The average dose of insulin administered was 29.6 ± 11.6 IU and the number of days of hospital stay was 9.3 ± 5 days. The reasons for admission to the hospital were: abscesses and soft tissue infection, hip fracture, diabetic foot, other fractures, cancer, heart disease, gastrointestinal bleeding, acute cholecystitis, stage IV chronic kidney disease, pneumonia, gonarthrosis, pathway infection urinary tract, intoxications, meningitis, alveolar obesity-hypoventilation syndrome, peripheral thrombosis and obstructive uropathy.

EFFECTIVENESS RESULTS

When evaluating efficacy, by protocol, the following was observed: The fasting glucose average in the "physiological" group was 130.3 ± 20.9 mg / dl, while in the traditional group it was 126 ± 22 mg / dl ($p = 0.114$); the average postprandial glucose in the physiological group was 150.8 ± 22.8 mg / dl and in the traditional group it was 149.4 ± 28.1 mg / dl ($p = 0.833$). The average morning glucose in the first group was 130.9 ± 18.3 mg / dl and 125.9 ± 26.7 mg / dl in the second group ($p = 0.081$).

In the analysis by intent to treat in the same way control was achieved in goals in both groups. The average fasting glucose in the "physiological" group was 135 ± 22.6 mg / dl, while in the traditional group it was 129.6 ± 23.6 mg / dl ($p = 0.114$); the average postprandial glucose in the physiological group was 156.2 ± 27.2 mg / dl and in the traditional group it was 155.4 ± 29 mg / dl ($p = 0.902$). The average morning glucose in the first group was 136.2 ± 21.2 mg / dl and 127.4 ± 26.6 mg / dl in the second group ($p = 0.081$).

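### Fasting and morning glucose carry identical p-values in the per-protocol and intention-to-treat analyses (0.114 and 0.081) although every input differs; at least one value in each pair appears carried over

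*Combined protocol and SAP*

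**What the plan says.** The Statistical Analysis section says that for numerical variables "the t test was used for two independent samples or its non-parametric version", depending on the distribution. It does not say which test was applied to which outcome. It sets the threshold ("A p value <0.05 was considered significant") and provides for both a per-protocol and an intention-to-treat (ITT) analysis.

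Patients of the Study gives 28 physiological patients per protocol, and "31 patients in the traditional group were completed in the analysis per protocol". The ITT set has 36 and 39.

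Effectiveness Results then gives, for the traditional group:

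- Fasting, per protocol: "it was 126 ± 22 mg / dl ($p = 0.114"), against 130.3 ± 20.9 in the physiological group.
- Fasting, ITT: "it was 129.6 ± 23.6 mg / dl ($p = 0.114"), against 135 ± 22.6.
- Morning, per protocol: "125.9 ± 26.7 mg / dl in the second group ($p = 0.081"), against 130.9 ± 18.3.
- Morning, ITT: "127.4 ± 26.6 mg / dl in the second group ($p = 0.081"), against 136.2 ± 21.2.

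**The concern.** A p-value depends on the data in its own analysis set. Here the ITT set has 75 patients and the per-protocol set 59, so 16 patients enter one analysis and not the other. Every printed mean and SD changes, as do both differences. Yet both p-values repeat to the third decimal.

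The other numerical outcomes reported for both sets do not repeat: postprandial glucose 0.833 and 0.902, days to control 0.553 and 0.445, hypoglycemic events per affected patient 0.129 and 0.182. The one other repeat, p = 1.0 for mild hypoglycemia, is a categorical comparison at the upper limit of p, where repetition is unremarkable.

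At stake is the accuracy of reported efficacy results: if a value was carried over, at least one p-value for each of these two outcomes does not belong to the data printed beside it.

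**Working it through.** **Inputs.** Means and SDs come from Effectiveness Results, and group sizes from Patients of the Study (28/31 and 36/39). No group size is given per outcome, so I assume that these apply to each average.

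**Formula (Student t).** Pooled SD s = √{[(n₁−1)s₁² + (n₂−1)s₂²]/(n₁+n₂−2)}; SE = s·√(1/n₁ + 1/n₂); t = difference/SE on n₁+n₂−2 degrees of freedom, two-sided.

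**Step 1: reproduce figures that are not duplicated (postprandial glucose).**

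- Per protocol: 150.8 − 149.4 = 1.4; s = 25.73; SE = 6.71; t = 0.209 on 57 df; p = 0.835 (Welch 0.834). Printed 0.833; the range allowing for rounding of the printed summaries is 0.823–0.847.
- ITT: 156.2 − 155.4 = 0.8; s = 28.15; SE = 6.51; t = 0.123 on 73 df; p = 0.902 (Welch 0.902). Printed 0.902.

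For this outcome the method and the group sizes reproduce the document.

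**Step 2: the four repeated values.**

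| Outcome, set | Difference | SE | t (df) | p (rounding range) | Welch p | Printed p | Difference needed for printed p |
|---|---|---|---|---|---|---|---|
| Fasting, per protocol | 4.3 | 5.60 | 0.768 (57) | 0.446 (0.384–0.512) | 0.445 | 0.114 | 9.0 |
| Fasting, ITT | 5.4 | 5.35 | 1.010 (73) | 0.316 (0.268–0.368) | 0.315 | 0.114 | 8.6 |
| Morning, per protocol | 5.0 | 6.02 | 0.830 (57) | 0.410 (0.400–0.420) | 0.402 | 0.081 | 10.7 |
| Morning, ITT | 8.8 | 5.58 | 1.576 (73) | 0.119 (0.115–0.124) | 0.116 | 0.081 | 9.9 |

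None of the four is reproduced. Halving for a one-sided test gives 0.223, 0.158, 0.205 and 0.060, which do not match either.

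**Step 3: how much weight a mismatch can bear.** Days to control also misses the t test: recomputed 0.741 per protocol (printed 0.553) and 0.696 ITT (printed 0.445), both outside their rounding ranges of 0.61–0.87 and 0.55–0.85. Those two printed values are not duplicated, and a rank test is permitted. A mismatch with the t test is therefore not proof of error, and Step 2 is supporting evidence only.

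**Step 4: could a rank test give the same p-value twice?** Each printed value is attainable at both sets of group sizes but corresponds to essentially one Mann-Whitney U (normal approximation, no ties, no continuity correction): 0.114 at U = 330 per protocol and U = 553 ITT; 0.081 at U = 319 and U = 537.5. To judge how often the two sets would agree, the per-protocol patients were simulated as a subset of the ITT patients, matched to the printed means and SDs of both sets, with 6000 runs for each of three assumed shapes (normal, log-normal with σ 0.3, log-normal with σ 0.6). Per-protocol and ITT p-values agreed to three decimals in 1, 0 and 11 runs for fasting, and in 0, 0 and 0 runs for morning. The document shows agreement for both outcomes.

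**The case against.** The strongest defense is that the plan permits a rank test and the summaries do not determine a rank-test p-value, so no single printed value is shown to be impossible. That stands. In particular, 0.081 is an ordinary rank-test result for morning glucose in ITT: near-normal simulated data gave a 95% range of about 0.05 to 0.28. What the defense does not explain is the repetition for two outcomes across different data.

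Three stronger readings are tempting, and the documents support none of them.

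- **That the per-protocol values are the wrong ones.** They lie further from the t test than the ITT values, which makes copying from ITT to per protocol the likelier direction. But the test used is not named, so the direction is not established.
- **That a significant difference in morning glucose is hidden.** All printed and t-test values exceed 0.05. In the simulations the morning ITT rank-test p fell below 0.05 in 1.5% of normal runs, 21.7% with σ 0.3 and 73.5% with σ 0.6, so a crossing in practice needs both a rank test and appreciable skew. The documents show neither. The plan says that "mean and standard deviation or median and interquartile range (Q1 to Q3) were reported according to the distribution of the data", and these outcomes are given as mean ± SD, which, if anything, points to approximate normality. If the ITT value is correct and the per-protocol one is wrong, the corresponding shares are 0%, 0.2% and 11.9%.
- **That the trial presents the matching p-values as agreement between the two analyses.** It does not. The ITT paragraph's remark about achieving control in both groups concerns glycemic targets.

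**Conclusion.** The point holds, as a minor one. At least one p-value in each of the two pairs appears to have been carried over from the other analysis. Confidence in this is high because it rests on the duplication itself. Which member of each pair is wrong, and what the correct values are, cannot be settled from the documents.

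If t tests were used, the values are near 0.446 and 0.316 for fasting and 0.410 and 0.119 for morning, so all four printed values would be too small and the non-significant reading would be unchanged. These figures assume the stated group sizes for every outcome; fewer contributing patients would raise the t-test p-values and widen the gap. If rank tests were used, the correct values need the patient data. The simulated frequencies depend on the assumed distribution shapes.

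The point does not touch the design, the planned method, the hypoglycemia outcome behind the sample size or the sustained-control result.

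**What to change.** Recompute the four p-values (fasting and morning glucose, per protocol and ITT) from patient-level data, running each set separately. State for each whether the t test or the rank test was used, and correct the printed values in Effectiveness Results. If a recomputed value falls below 0.05, the description of that outcome must follow it.

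The cost is a re-run of four two-group comparisons and a correction to two paragraphs. It needs no new data and no change to the stated analysis method.

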The number of days to reach control during the hospital stay statistically were not different between groups (by protocol 4.9 ± 2.2 days vs 4.7 ± 2.4 days, $p = 0.553$, by intention to treat 4.9 ± 2.1 days vs 4.7 ± 2.3 days, $p = 0.445$).

SAFETY RESULTS

Safety was evaluated with episodes of hypoglycemia and complications associated with diabetes. In the "physiological" group it was observed that 15 (41.6%) patients had at least one event of hypoglycemia during their entire stay; On the other hand, in the traditional group 15 (38.4%) presented at least one event of hypoglycemia (per protocol, RR: 1.11, 95% CI: 0.62 to 1.97, $p = 0.729$; intention to treat, RR = 1.08, 95% CI: 0.62 to 1.89, $p = 0.777$). The presence of more than 2 hypoglycemic events during their hospitalization was observed in 8 (22.2%) patients of the "physiological" group and in 2 (5.1%) patients of the traditional group (per protocol, RR = 7.75, 95% CI: 1.02 a 59.13, $p = 0.021$; by intention to treat, RR: 4.33, 95% CI: 0.98 to 19.07, $p = 0.041$).

In the analysis by protocol, the rate of the number of total events / patients with hypoglycemia in the "physiological" group was 2.4 ± 1.3 events / patient, while in the traditional group it was 1.6 ± 0.7 events / patient ($p = 0.129$) ; in the intention-to-treat analysis in the "physiological" group it was 2.5 ± 1.6 events / patient, whereas in the traditional group it was 1.7 ± 0.9 events / patient ($p = 0.182$).

Thirty-eight hypoglycemic events were found in the "physiological" group and 26 hypoglycemic events in the traditional group; of which, 36 were mild hypoglycemia in the "physiological" group and 24 events in the traditional group (RR per protocol: 1.02, 95% CI: 0.91 to 1.19, $p = 1.0$; RR by intention to treat: 1.03, 95% CI: 0.90 to 1.17, $p = 1.0$).

Regarding the complications associated with diabetes, soft tissue infection was the most frequent, one patient had pneumonia, one acute renal failure, one acute

respiratory failure, and no patient presented bacteremia, diabetic ketoacidosis or hyperosmolar state. Two of the patients included in the study died from complications not associated with hypoglycemia, one in the physiological group secondary to progression of the infectious process, sepsis and septic shock, and one in the group Traditionally associated with acute respiratory failure.

SECONDARY RESULTS

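### The intention-to-treat statement that control was achieved in both groups rests on mean glucose and p values, while the patient flow shows at least 12 of 75 patients left or died before control

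*Combined protocol and SAP*

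**What the plan says.** Effectiveness Results gives fasting, postprandial and morning glucose as mean ± SD with a p value, first per protocol and then by intention to treat. The second paragraph opens: "In the analysis by intent to treat in the same way control was achieved in goals in both groups". It gives no count of patients at goal and no confidence interval for any glucose difference. The same section adds: "The number of days to reach control during the hospital stay statistically were not different between groups".

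Patients of the Study puts 36 physiological and 39 traditional patients in the intention-to-treat set. It then lists those who left. In the physiological arm, "6 patients did not conclude the treatment by discharge before the control" and 2 more had poor adherence. In the traditional arm, "5 patients withdrew before the control", "1 patient died before the control", 1 had poor adherence and 1 became critical. That leaves 28 and 31 per protocol.

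Secondary Results reports "sustained control of blood glucose that was reported in 20 (55.6%) of the cases in the physiological group" against 30 (76.9%) in the traditional group. Among the causes of failure it names discharge before reaching goal and death before glycemic control.

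Statistical Analysis plans a t test or its non-parametric counterpart for numerical variables, and 95% CIs for the risk measures only. No margin for glucose is set. Sample Size is built on a 25% difference in hypoglycemia, not on glucose.

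**The concern.** A group mean below some level does not show that the patients in the group reached control. Here the report's own flow identifies patients in the intention-to-treat set who did not. The set is described as controlled in one section, and some of its members are counted as failures in another.

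The title question is glycemic control, so this sentence is the one a reader will carry away. Without a count of patients reaching control, or an interval for the mean differences, the reader cannot tell how many patients each scheme controlled or how large a difference the data leave open. Days to control by intention to treat has a related gap: the report does not say how patients who left before control entered that average.

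**Working it through.** **1. Patients who left before control (Patients of the Study).**
- Physiological: 6 discharged before control; 6/36 = 16.7%.
- Traditional: 5 withdrew + 1 died before control = 6; 6/39 = 15.4%.
- Together 12/75 = 16.0%. This is a minimum: 3 patients with poor adherence (2 and 1) and 1 critical patient also left, with control status not stated, making 16 of 75 exits.

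**2. Consistency with Secondary Results.**
- Physiological: 36 - 6 - 2 = 28; less 8 with the scheme suspended or changed = 20, the printed sustained-control count.
- Traditional: 39 - 5 - 1 - 1 - 1 = 31; less 1 suspended or changed = 30, again the printed count.

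So the exits in step 1 are counted there as failures of sustained control. That result reproduces: RR = (20/36)/(30/39) = 0.72 (0.51 to 1.01), chi-square p = 0.0499 (printed 0.049), risk difference -21.4 points (-42.3 to -0.4).

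**3. What the flow implies for reaching control.** Two cases, both assuming that every per-protocol patient reached control, which the report does not state:
- The four patients of unknown status counted as controlled: 30/36 (83.3%) v 33/39 (84.6%), difference -1.3 points (-17.9 to 15.3).
- The four counted as not controlled: 28/36 (77.8%) v 31/39 (79.5%), difference -1.7 points (-20.3 to 16.9).

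Neither case suggests a difference between arms, and both intervals are wide.

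**4. Printed p values.** Pooled t test, with s² = [(n1-1)s1² + (n2-1)s2²]/(n1+n2-2), SE = s√(1/n1 + 1/n2), t = difference/SE:

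| Set | Outcome | Physiological | Traditional | Printed p | Pooled t p |
|---|---|---|---|---|---|
| Per protocol (28 v 31) | fasting | 130.3 ± 20.9 | 126 ± 22 | 0.114 | 0.446 |
| | morning | 130.9 ± 18.3 | 125.9 ± 26.7 | 0.081 | 0.410 |
| | postprandial | 150.8 ± 22.8 | 149.4 ± 28.1 | 0.833 | 0.835 |
| ITT (36 v 39) | fasting | 135 ± 22.6 | 129.6 ± 23.6 | 0.114 | 0.316 |
| | morning | 136.2 ± 21.2 | 127.4 ± 26.6 | 0.081 | 0.119 |
| | postprandial | 156.2 ± 27.2 | 155.4 ± 29 | 0.902 | 0.902 |

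The postprandial values reproduce (Welch gives 0.834 per protocol). The fasting and morning values do not, by pooled, Welch, normal or one-sided versions. They are also identical across two sets whose means, SDs and sizes differ. A non-parametric test cannot be checked from summary data.

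**5. Intention-to-treat mean differences.** Difference ± t(0.975, 73) × SE, with t = 1.993:
- Fasting: s = 23.13, SE = 5.35; +5.4 ± 10.65 gives -5.3 to 16.1 mg/dl.
- Morning: s = 24.16, SE = 5.58; +8.8 ± 11.13 gives -2.3 to 19.9.
- Postprandial: s = 28.15, SE = 6.51; +0.8 ± 12.97 gives -12.2 to 13.8.

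**6. Sensitivity to the p values.** If the SE is instead back-calculated from the printed p values, the upper limits become about 12.1 (fasting) and 18.7 (morning).

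**The case against.** The strongest defense is that the sentence is only a loose transition: by intention to treat, likewise, mean glucose was acceptable in both arms. Secondary Results then gives a patient-level outcome on 36 and 39, with a CI, that counts leavers and deaths as failures and openly favors the traditional arm. Reaching control and sustaining it are different outcomes, so the lower sustained-control rate does not by itself refute the sentence.

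Much of this stands.
- A reader might infer a claim of equivalent control. The linking phrase most naturally means that the result matched the per-protocol one. The document nowhere claims equivalence or non-inferiority, so a missing margin is not a fault in a claim it does not make.
- A reader might infer from the early exits that one scheme controlled fewer patients. They split 6 and 6 and show no such thing.
- A reader might take the upper limits of 16 and 20 mg/dl as a demonstrated deficit of the physiological scheme. All three intervals include zero, and those limits are the unfavorable ends of two of them.
- A reader might estimate the share of patients above 140 or 180 mg/dl from the means and SDs. The document uses those values to trigger dose changes and supplements and does not label them as goals. The averaging window is not stated either, and a patient's stay average does not show whether control was eventually reached.

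What does not stand is the sentence itself. Even read as likewise, it says that control was achieved in the intention-to-treat set. It might be argued that control in the flow paragraph means a follow-up check, but the causes of failure in Secondary Results refer explicitly to goals and glycemic control. The sustained-control result does not say how many patients ever reached control.

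**Conclusion.** The point holds as a contradiction between an efficacy statement and the patient flow. At least 12 of 75 (16.0%) in the intention-to-treat set left or died before control, and mean glucose with p values above 0.05 cannot show otherwise. The data support a statement about mean glucose with no difference detected. They do not support a statement that control was achieved, or that control was similar.

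The count rests on reading control in the flow paragraph as glycemic control. The intervals rest on the printed means, SDs and group sizes being right. That is in some doubt for fasting and morning glucose, because the printed p values disagree with them. A copying error between the two analysis sets is plausible but not established. Whether differences of the size left open matter clinically is a judgment that the document gives no basis for settling.

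**What to change.** 1. Check the fasting and morning p values for both analysis sets against the source output, and state which test produced each.
2. Replace the sentence with one about mean glucose only, concluding that no difference was detected.
3. State the definition of control that the trial used. By arm, report the number who reached control out of 36 and 39, counting those who left or died before control as not controlled, with risk difference and 95% CI. Place this next to the sustained-control result.
4. Add the mean difference with 95% CI for each glucose outcome. The step 5 values can stand if the means and SDs are confirmed.
5. State how patients who never reached control were handled in the days-to-control averages.

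The cost is re-tabulation of data already collected and a few changed sentences. No new data or change to the trial's conduct is involved.
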